Title of Project: The effects of antenatal and perinatal education of labor analgesia options on maternal anxiety, labor analgesia and maternal satisfaction

Principal Investigator: [name]

Funding Source(s): NJMS Anesthesiology Department

1. Purpose/Specific Aims

The specific aim of the study is to determine if education in the antenatal period and repeated upon arrival to Labor and Delivery regarding labor analgesia options is useful in reducing maternal anxiety and improving patient satisfaction.

1.1 Objectives

The study objectives are as follows:

1. To educate patients as to the various options available to them for labor analgesia.
2. To determine if the education material provided is helpful to patients in choosing a preference for a particular analgesia modality.
3. To determine if the education provided is helpful in reducing maternal anxiety.

1.2 Hypotheses

The hypothesis is that providing written material regarding labor analgesia options will improve maternal satisfaction and lessen anxiety in regard to labor.

2. Background and Significance

Background

Many analgesic options exist for laboring parturients, but labor may not be the best time to start informing patients of their options. Many patients begin the labor process with a plan in place for their analgesia. Unfortunately, internet resources regarding labor analgesia that are available to the lay parturient are poor and often lead to misconceptions about the options and their risks. A significant number of patients refuse neuraxial analgesia based on misunderstandings, concerns about the procedure, or a lack of faith in the provider. Some women want a “natural childbirth” and/or control over their labor experience. Forty-seven percent of minority women feel inadequately educated about anesthesia, are less likely to trust physicians, and are less likely to receive epidurals. However, greater than 10% of obese women changed their preference toward epidural analgesia following antenatal consultation. Also, 50% of patients planning for analgesia-free labor request neuraxial analgesia after experiencing labor pain.³

Additionally, the question exists as to the quality of informed consent from a patient undergoing contraction pain and possible sedation from analgesic medications. The

RUTGERS APPROVED

THE STATE UNIVERSITY OF NEW JERSEY

Protocol Version: 20150001/531

Approval Date: 4/30/2015

Expiration Date:

Add protocol title
PI name

consensus is that parturients can provide informed consent. However, the process of informed consent for labor analgesia is not standardized; the options and risks presented to patients are dependent upon the individual practitioner obtaining the consent. Regarding epidurals, patients want to be informed of all risks and complications associated with the procedure.⁵ The patient's recall of the risks and benefits of the epidural procedure improved by 50% with written material in addition to verbal discussion, and recall improved by more than a factor of five when consent during labor was preceded by antenatal education. Parturients want a "pre-operative" visit with an anesthesiologist and have a strong desire for pre-labor education of anesthesia/analgesia options. Early antenatal education allows for unpressured time to teach, relieves anxiety, develops rapport, and provides opportunities for additional testing, if needed.³ Finally, the timing of epidural placement has not been shown to change outcomes, but when initiated late in the labor process, often other analgesia modalities were used that confounded the analysis of outcomes. Therefore, earlier request, which may come with prior knowledge and avoidance of misconceptions, and earlier placement of epidurals may lead to fewer analgesic interventions in the parturient and possibly less morbidity for the patient and fetus.

3. Research Design and Methods

This is a prospective study where written educational material will be dispensed to women when they visit the antenatal clinic during the course of their gestational visits. The material will again be provided upon admission to Labor and Delivery and a conversation will take place with the anesthesia care provider regarding the options for analgesia.

3.1. Duration of Study

The study will commence upon receipt of the written educational material in the subject's preferred language. The material will provide a second time upon arrival to the Labor and Delivery Suite and at that time a discussion will be held with the anesthesia care provider regarding the options and their risks and benefits for analgesia and anesthesia for labor and delivery (15-20 minutes). The study will end following delivery when the subject completes the survey on the post-partum unit on F Green. The survey is expected to take 10-15 minutes.

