3.3 Sample Size Justification

We aim for the completion of 100 surveys which will believe will provide us with information to establish as to whether or not this written literature is an effective method in reducing anxiety and improving patient satisfaction.

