3.4 Subject Selection and Enrollment Considerations

RUTGERS APPROVED

Protocol Version 1.0 - 04/21/15

IRB ID: Pro20150001531

Approval Date: 4/30/2015

Expiration Date:

Add protocol title
PI name

All comers to the antenatal clinic and labor and delivery unit will receive the same educational information. Those women who are not English or Spanish speaking will not be provided with the written educational material and information letter.

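### Sections 1.2 and 3.3 promise a conclusion about the written material, but the plan delivers a pamphlet-plus-discussion package with no comparator or stated baseline, so only a description of the package is possible

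*Protocol*

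**What the plan says.** The Protocol describes what is being evaluated in two ways.

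- **Written material alone.** Section 1.2 hypothesises that "providing written material regarding labor analgesia options will improve maternal satisfaction and lessen anxiety in regard to labor". Section 3.3 sets the target ("We aim for the completion of 100 surveys") and expects it to establish "whether or not this written literature is an effective method in reducing anxiety and improving patient satisfaction".
- **A package.** Section 3 (Research Design and Methods) has the pamphlet given antenatally and again on admission, when "a conversation will take place with the anesthesia care provider regarding the options for analgesia". Section 3.1 repeats this ("at that time a discussion will be held with the anesthesia care provider regarding the options and their risks and benefits") and gives 15-20 minutes for it.

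The specific aim in Section 1 and objective 3 in Section 1.1 use the wider term, education, which can cover both components. Section 4.1, where the intervention would be defined, is marked not applicable.

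On exposure, Section 3.4 states that "All comers to the antenatal clinic and labor and delivery unit will receive the same educational information". Inclusion criterion 3 (Section 3.5.1) requires the pamphlet, in pregnancy or in labor, and does not mention the discussion. Outcomes come from one anonymous questionnaire after delivery (Sections 3.1, 4.2 and 5). Women are first approached for consent on the postpartum unit (Section 3.5.4), and no earlier measurement is stated.

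**The concern.** The hypothesis and the sample-size section credit one component of a package. A conversation with the anesthesia provider about options, risks and benefits could plausibly affect the same two outcomes, anxiety and satisfaction. The Protocol's own background treats written and verbal information as distinct, since it cites better recall when written material is added to verbal discussion.

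If the plan is followed as written, a favorable survey would be reported as showing that the literature works. A clinic might then adopt the pamphlet without the conversation, on evidence that never separated the two. The survey is anonymous and keeps no link to identifiers, so information on who had which component cannot be recovered later if it is not asked at the time.

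**Working it through.** **The plan's own figure.** The target of 100 surveys cannot be reproduced, because Section 3.3 gives no error rate, power, effect size or variability. The question here is attribution, so the check is which effects the design can estimate.

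**Model.** Write a woman's expected score as b0 + bP·P + bD·D, where P = 1 if she had the pamphlet, D = 1 if she had the discussion, and b0 is the score she would have had with neither.

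**Design as planned (Sections 3, 3.1 and 3.4).** P = D = 1 for all 100 women. The columns for the intercept, P and D are identical, so the design matrix has rank 1 with 3 unknowns. The survey estimates only the sum b0 + bP + bD. Neither bP nor bP + bD can be extracted from it at any sample size.

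**Variations, to see what each obstacle contributes:**

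| Design | What is estimable | Pamphlet effect bP? |
|---|---|---|
| As planned | b0 + bP + bD | No |
| Discussion removed, all have the pamphlet | b0 + bP (rank 1 of 2) | No |
| Baseline added to the plan | change over time + bP + bD | No |
| Control with neither component | bP + bD | No |
| Control with discussion, no pamphlet | bP (rank 2 of 2, D constant) | Yes |

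Row 2 shows that the missing comparator is enough to block the conclusion without the discussion. Rows 3 and 4 show that the bundled discussion still blocks it after some repairs to the comparator. Only the last row removes both obstacles.

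**If some women missed the discussion.** Criterion 3 allows this. With D varying and recorded, the columns (1, P, D) have rank 2 of 3. A non-randomized contrast on D becomes estimable, but P is still 1 for everyone surveyed and remains inseparable from the intercept. Women who do not read English or Spanish are not given the pamphlet, but they are excluded from the survey (Sections 3.4 and 3.5.2), so they supply no contrast.

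**What 100 surveys do give.** The 95% half-width for a proportion near 50% is 1.96 × √(0.25/100) = 0.098, or 9.8 percentage points. For a mean it is 1.96/√100 = 0.196 SD, about 0.20 SD. Both describe women who received the package.

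**Context for the last table row (assumed, not in the Protocol).** Take 50 women per group and two-sided alpha 0.05, with power = Φ(d·√(50/2) − 1.96) = Φ(5d − 1.96).
- d = 0.3 SD: Φ(−0.46), about 32%.
- d = 0.5 SD: Φ(0.54), about 71%.
- d = 0.566 SD: Φ(0.87), about 81%.

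**The case against.** The strongest reply is that this is a local wording slip. The aim and objective 3 already speak of education, and only Sections 1.2 and 3.3 are narrower. On this view the real defect is the missing comparator, which defeats the pamphlet claim by itself, and the discussion may be part of usual consent practice, in which case an ordinary usual-care control would isolate the pamphlet.

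Much of this stands. The broader framing exists, and the missing comparator is a sufficient obstacle. The Protocol does not say whether the discussion is usual care, but it lists it among the study steps. Even if it is usual care, no surveyed group lacks the pamphlet. The mismatch still matters, because Sections 1.2 and 3.3 are where the conclusion to be drawn is stated. No analysis plan can separate components that everyone received or recover exposure that was not collected.

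A reader might infer several stronger things that the documents do not support:

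- *That the discussion alone prevents the conclusion, or that any added control would still test only the package.* The table shows otherwise on both counts.
- *That pamphlet and discussion are perfectly collinear among the women surveyed.* That describes the plan. Eligibility requires only the pamphlet, so actual exposure to the discussion may vary.
- *That the pamphlet's share of any benefit lies between 0% and 100%.* This is not a valid bound. Both components convey risks, so one could raise anxiety while the other lowers it.
- *That the discussion is one-to-one, or known to be a strong influence.* The Protocol says neither.

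**Conclusion.** The point holds in a limited form. Following the plan exactly, the study cannot establish that written material reduces anxiety or improves satisfaction. This is a failure of identification, so it has no numerical size and no sample size cures it. The 100 surveys can support a description of the package's recipients, to within about 9.8 percentage points or 0.20 SD.

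The conclusion assumes that the design is as Sections 3 to 3.5 describe it, with one surveyed group, one post-delivery questionnaire and no baseline. The questionnaire itself is not shown. Section 4.2 says it covers thoughts about the pamphlets and overall satisfaction with analgesia, so it may already hold some of the exposure items suggested below. Women's opinions of the pamphlet can be reported whatever the design, but they measure perceived usefulness and do not show an effect on anxiety.

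Replacing written material with education package would not be enough by itself. A single post-delivery survey cannot show that the package reduced anxiety either, so the reworded claim must be descriptive.

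**What to change.** 1. Reword Sections 1.2 and 3.3 to match the specific aim. The study describes women's reported anxiety, satisfaction and perceived helpfulness after the education package (antenatal pamphlet, repeat pamphlet and provider discussion). State that no causal claim will be made for the package and no claim for the pamphlet alone.
2. If the questionnaire does not already ask, add tick-box items on whether the woman read the pamphlet before labor, whether she had the discussion, and how helpful she found each. Report these side by side, as perceived helpfulness only.

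The cost is two wording changes, a few items on a survey now expected to take 10-15 minutes, and a narrower conclusion. If the sponsor wants to keep a claim about the pamphlet itself, that is a different study. It would need a concurrent group that has the discussion without the pamphlet, and a sample size justified for that comparison.

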3.2 Study Sites

Components of the study will be done in 3 different locations: The study will be conducted at the antenatal clinic area, Labor and Delivery Suite UH F Orange and the UH Post-partum Unit F Green.

3.3 Sample Size Justification

We aim for the completion of 100 surveys which will believe will provide us with information to establish as to whether or not this written literature is an effective method in reducing anxiety and improving patient satisfaction.

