3.5.1 Inclusion Criteria

1. Postpartum women ages 18 and older
2. Patients who speak and read English or Spanish
3. Patients who received our informational pamphlet while pregnant or in labor
4. Patients who are able to consent and make medical decisions
5. Patients undergoing labor or trial of labor after cesarean delivery
6. Patients who undergo cesarean delivery after trial of labor

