3.5.2 Exclusion Criteria

1. Patients unable or unwilling to complete questionnaire
2. Patients unable to consent or make medical decisions
3. Patients less than 18 years of age
4. Patients unable to read and speak English or Spanish
5. Patients in whom any of the analgesic options were contraindicated
6. Patients with a history of an anxiety disorder
7. Patients with precipitous labor or late presentation that precluded an analgesic intervention
8. Patients with fetal distress that precluded an analgesic intervention
9. Patients planned for elective cesarean section.

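### Section 3.3 says 100 surveys will establish whether the pamphlet works, but every surveyed woman received it and no comparison is described

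*Protocol*

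**What the plan says.** The comparative claim appears in several places in the protocol:

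- Section 1 asks "if education in the antenatal period and repeated upon arrival to Labor and Delivery regarding labor analgesia options is useful in reducing maternal anxiety"; satisfaction is named as the second outcome.
- Section 1.2 hypothesises that "providing written material regarding labor analgesia options will improve maternal satisfaction and lessen anxiety in regard to labor".
- Section 3.3 justifies the target of 100 completed surveys by the belief that they will "provide us with information to establish as to whether or not this written literature is an effective method in reducing anxiety"; it makes the same claim for satisfaction.
- Section 4.2 says the analysis will look at the utility and effect of the materials on informed consent, choice of modality and anxiety.

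The design is set out as follows:

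- **Exposure.** Section 3.5.1, criterion 3, admits "Patients who received our informational pamphlet while pregnant or in labor". Section 3.4 gives the same information to all comers, with one exception: "Those women who are not English or Spanish speaking will not be provided with the written educational material". Section 3.5.2, criterion 4, excludes "Patients unable to read and speak English or Spanish".
- **Measurement.** Section 3.1: "The study will end following delivery when the subject completes the survey on the post-partum unit". Section 4.2 places the questionnaire after delivery. No earlier measurement is described.
- **Linkage.** Section 5 makes the survey anonymous and keeps no link to identifiers.
- **Co-intervention.** When the pamphlet is given again on Labor and Delivery, Section 3.1 adds that "at that time a discussion will be held with the anesthesia care provider", lasting 15-20 minutes.
- **Analysis.** Section 5 reports means, standard deviations and percentages. It names a t test and chi-square for demographic data only and defines no groups.

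**The concern.** To say that something reduces anxiety or improves satisfaction is to compare it with what would have happened otherwise. The protocol makes that claim, and uses it as the only justification for the sample size, but its design supplies nothing to compare with. Exposure does not vary among the women surveyed, the outcome is measured once, and no norm, historical rate or threshold is given.

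This is not a detail that a statistical analysis plan could settle. A plan can choose tests and models, but it cannot supply a group or a baseline that the protocol does not collect.

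What is at stake is the study's main conclusion. A high percentage satisfied, or a high percentage reporting less anxiety, would be the recipients' own report. Section 3.3 would allow it to be presented as evidence that the pamphlet works, and Section 7.3 plans presentation at national meetings.

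**Working it through.** **The plan's own figure.** The 100 in Section 3.3 cannot be reproduced. The section gives no effect size, SD, expected rate, reference value, error rate, power or precision target. The check is therefore which quantities 100 such surveys can estimate.

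**Possible sources of a contrast, taken in turn**

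1. *Women without the pamphlet.* Criterion 3 of 3.5.1 requires receipt. The women whom 3.4 leaves without it are removed by criterion 4 of 3.5.2. There is no such group.
2. *Before and after.* One questionnaire after delivery (3.1, 4.2), anonymous and unlinked (Section 5). There is no separate baseline, and answers cannot be matched to an earlier record.
3. *External reference.* None is stated.
4. *Antenatal versus labor-only receipt.* Criterion 3 allows both, but no such comparison is described. Section 3.5.3 leaves pamphlets in the clinic waiting area, so who has one before labor would largely be self-selected. The contrast touches the timing part of the Section 1 aim, not whether the pamphlet works.
5. *Written material alone.* Where 1.2 and 3.3 single out written material, its contribution cannot be separated from that of the provider discussion in 3.1. Sections 1 and 1.1 speak of education, so this step does not apply to them.

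**What 100 surveys can describe**

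Proportion, 95% half-width = 1.96 × √(p(1 − p)/n):

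| n | p (assumed) | Half-width |
|---|---|---|
| 100 | 0.5 (worst case) | 1.96 × √(0.25/100) = 0.098 |
| 100 | 0.7 | 1.96 × √(0.21/100) = 0.090 |
| 100 | 0.8 | 1.96 × √(0.16/100) = 0.078 |
| 80 | 0.5 | 1.96 × √(0.25/80) = 0.110 |
| 1,000 | 0.8 | 1.96 × √(0.16/1,000) = 0.025 |

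Mean, 95% half-width in SD units = t(0.975, n − 1)/√n. For n = 100 this is 1.984/10 = 0.198, and for n = 80 it is 0.223. The rows with n = 80 allow for unanswered items.

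**What they cannot estimate**

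Assume 80 of 100 are satisfied. The Wilson 95% interval for the level is 0.711 to 0.867. Write the effect as 0.80 − r, where r is the rate had these women not received the pamphlet. The data say nothing about r, which may lie anywhere from 0 to 1:

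- lower bound: 0.80 − 1 = −0.20
- upper bound: 0.80 − 0 = +0.80
- width: 0.80 − (−0.20) = 1.00, and n does not enter

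Going from 100 to 1,000 surveys cuts the half-width of the level from 7.8 to 2.5 points and leaves the width of the effect range at 100 points.

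**If the form asks about change in anxiety** (assumed; the form is not shown). An exact two-sided 5% test of the share reporting less anxiety against 50%, with n = 100, rejects at 39 or fewer or 61 or more (actual size 0.035). Power is 0.46 at a true share of 0.60, 0.83 at 0.65 and 0.98 at 0.70. A significant result would concern recalled change among recipients, not a difference from no pamphlet.

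**The case against.** The strongest reply is that this is a perception survey with a loosely worded aim. Objective 2 in 1.1 asks whether the material helps patients choose, 4.2 asks for their thoughts about the pamphlets, and Section 5 is descriptive. Section 3.3 states only a belief and names no test. That reading of the conduct of the study is right, and it is why the wording has to change and not the survey. But the same comparative language stands in 1, 1.2 and 4.2, and the belief in 3.3 is the only support offered for the 100.

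The unseen questionnaire may ask women to compare their anxiety before and after reading. That would give a recalled within-person contrast, so only a separate baseline can be called absent. It would still be self-report among recipients. Likewise, the tests named in Section 5 might imply a comparison by time of receipt. The fair statement is that none is described.

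The bounds follow from any single-group result and rest on an assumed 80%. They show only that sample size is not the remedy. The protocol sets no precision target, so calling 100 adequate for description is a judgement. The half-widths cover sampling error only, and 3.5.2 excludes women unwilling to answer.

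On severity, no change to recruitment or data collection follows, which argues for a lower grade. Against that, the sentence at fault states what the study is meant to conclude.

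**Conclusion.** The concern holds. Section 3.3 ties 100 surveys to a finding of effectiveness that the described design cannot deliver at any sample size. The surveys can describe recipients' satisfaction, how helpful they found the education and, if the form asks, whether they felt less anxious. The structural conclusion rests on the eligibility rules and the single post-partum measurement alone. The 80% result, the 80 respondents per item and the true shares of 60% to 70% are illustrative assumptions, since the protocol gives none. The wording should be corrected before any result is reported.

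**What to change.** Delete the claim in 3.3 to establish effectiveness, and restate Sections 1, 1.2, 3.3 and the effect wording in 4.2 as descriptive. Objective 3 in 1.1 may stay if it is defined as perceived benefit. State three separate estimands, each as measured by the existing questionnaire:

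- (a) the level of satisfaction with labor analgesia;
- (b) the proportion who found the education helpful, including in choosing a modality and for informed consent;
- (c) the proportion who report that it reduced their anxiety.

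If the form has no item for one of these, drop that estimand or add the item. Section 3.3 could then read:

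> One hundred completed surveys estimate each proportion with a 95% half-width of at most about 10 percentage points, and a mean score to within about 0.2 SD. Results are recipients' own reports and are not evidence of effectiveness against no pamphlet.

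Label any split by antenatal versus labor-only receipt as exploratory and self-selected.

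The cost is a text amendment to an approved protocol, which may need re-approval, and a check of the form. No extra surveys or visits are needed. The price is a more modest claim. If the sponsor wants to keep the effectiveness claim, the design needs a pamphlet-free comparison or a measurement before the pamphlet, with a sample size to match, which is a much larger change.
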